11.5.2.1. Adverse Event Analyses

TEAEs are defined as those AEs with a start or worsening date during the on-treatment period.

AEs will be coded using MedDRA and graded based on v5.0 of NCI-CTCAE.

The number and percentage of subjects with TEAEs will be summarized by system organ class (SOC), and/or PT. Additional summaries will be provided by the worst CTCAE grade, relationship to the study treatment (ie, regardless of relationship to study drug, study drug related), seriousness, actions taken with study treatment (ie, associated with dose reduction, dose interruption, study treatment discontinuation), and fatality.

AESIs will also be summarized.

All deaths and on-treatment deaths will be summarized by primary cause of death. All deaths will be listed.

A by-subject AE (including TEAE) data listing will be provided including, but not limited to, verbatim term, PT, SOC, NCI-CTCAE grade, and relationship to study drug. SAEs, AESIs and TEAEs associated with treatment discontinuation will be listed.

SAEs starting or worsening after the on-treatment period, if reported as related to study treatment, will be listed separately.

11.5.2.2. Clinical Laboratory Evaluation Analyses

Descriptive statistics will be provided for clinical laboratory test results (hematology and chemistry) and changes from baseline by scheduled time of evaluation, including EOT. The baseline value is defined as the last non-missing value before the start of study treatment.

Abnormal laboratory results will be graded according to NCI-CTCAE v5.0, if applicable. A shift table, presenting the 2-way frequency tabulation for baseline and the worst post-treatment value according to the NCI-CTCAE grade, will be provided. Abnormal clinical laboratory test results that are deemed of clinical significance or of Grade 3 or 4 will be listed.

11.5.2.3. ECG

A listing of ECG data will be generated.

11.5.2.4. Vital Signs

Descriptive statistics will be provided for the vital sign measurements and the change from baseline by scheduled time of evaluation, including EOT. The baseline value is defined as the last non-missing value before the start of study treatment. A listing of vital sign data will be generated.

11.5.2.5. Other

Listings of all other safety endpoints (eg, physical examination findings including ECOG PS, ECHO/MUGA, and ophthalmologic findings) will be generated.

Immunogenicity (Anti-Drug Antibody) Analyses

Immunogenicity will be assessed through characterization of prevalence, incidence, and titer of ADA. The number and percentage of subjects with treatment-emergent ADA will be calculated. Treatment-emergent ADA positive is defined as subjects who were ADA negative at baseline and became ADA positive (ie, confirmed positive ADA) post-treatment or ADA positive at baseline and post-treatment and had an increase in ADA titer from baseline to post-treatment that meets the cut-off value of fold change or had missing ADA data at baseline and became ADA positive post-treatment. Concentrations and PK parameters of total anti-HER3 antibody, intact U3-1402 ADC, and released payload MAAA-1181a may be summarized by status of ADA, if data allow. ADA titer will be determined for samples confirmed ADA positive. When neutralizing antibody assay becomes available, confirmed ADA-positive samples may be analyzed for neutralizing activity.

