Study U31402-A-U102 is a multicenter, open-label, Phase 1 study of U3-1402 in subjects with metastatic or unresectable non-small cell lung cancer (NSCLC). This study includes a Dose Escalation Part in which subjects receive intravenous (IV) U3-1402 in 21-day cycles with a starting dose of 3.2 mg/kg, and a Dose Expansion Part in which subjects receive U3-1402 at the RDE determined in the Dose Escalation Part. As of the DCO date of 05 Aug 2019, 36 subjects had received U3-1402 in the Dose Escalation Part. Four subjects were enrolled in the 3.2 mg/kg cohort, 15 subjects were enrolled in the 4.8 mg/kg cohort, 12 subjects were enrolled in the 5.6 mg/kg cohort, and 5 subjects were enrolled in the 6.4 mg/kg cohort. At the DCO, 12 subjects were continuing study drug. Eighteen subjects had discontinued due to disease progression, 2 subjects due to clinical progression, 1 subject due to death caused by disease progression, 2 subjects due to an AE, and 1 subject had discontinued due to withdrawal of consent by subject. All (100%) subjects had at least one TEAE; nausea (23 [63.9%] subjects) and vomiting (15 [41.7%] subjects) were experienced by >40% of subjects. TEAEs of Grade 3 or higher were reported in 16 (44.4%) subjects as of 05 Aug 2019. The most common Grade ≥ 3 TEAEs reported in more than 5% of subjects included platelet count decreased (7 [19.4%] subjects), troponin increased (3 [8.3%] subjects), and anaemia and hypoxia (2 [5.6%] subjects each).

Preliminary efficacy data are available as of the previous DCO (May 2019) and are as follows: of the 26 efficacy-evaluable patients, 6 had confirmed partial responses (PRs; 2 each at 4.8, 5.6, and 6.4 mg/kg). Median best percentage change in sum of diameters (SoD) was -25.7% (range, -82.6% to 13.3%), including decreases in SoD in patients with CDK4 amplification (-25.7% and -17.8%), human epidermal growth factor receptor 2 (HER2) amplification (-28.6%), and both CCNE1 amplification and PIK3CA mutation (-28.8%).²⁹

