1.2.2. Benefit/Risk Assessment for Study Subjects

U3-1402 is being developed for the treatment of HER3-expressing malignant tumors.

Nonclinical studies have demonstrated the antitumor activity of U3-1402 in HER3 tumor-bearing mouse models. Thus, U3-1402 is hypothesized to demonstrate efficacy in treating HER3-expressing tumors in patients.

In nonclinical toxicology studies, intestinal toxicity, lymphatic/hematopoietic system toxicity, skin toxicity, pulmonary toxicity, reproductive and accessory organ toxicities, hepatic toxicity, cardiotoxicity, and renal toxicity were found in association with the administration of U3-1402.

As with any therapeutic Abs, there is a possibility of infusion-related reactions and immune responses causing allergic or anaphylactic reactions to U3-1402. Considering the toxicity data from the nonclinical studies, the important potential risk is hepatotoxicity, and the potential risks are infusion-related reaction, dry eye, keratitis, photosensitivity, dry skin, rash, rash maculopapular, and skin pigmentation in humans from exposure to U3-1402, and these have been closely monitored and evaluated in the U3-1402 clinical development program.

Based on the preliminary clinical safety data from the ongoing U3-1402 studies, the important identified risk is interstitial lung disease (ILD); the important potential risk is hepatotoxicity, and the identified risks are nausea, decreased appetite, platelet count decreased/thrombocytopenia, white blood cell count decreased/leukopenia, neutrophil count decreased/neutropenia, vomiting, anemia, diarrhea, fatigue, malaise, stomatitis, constipation, alanine aminotransferase (ALT) increased, AST increased, febrile neutropenia, and alopecia, and will continue to be closely monitored and evaluated in the U3-1402 clinical development program.

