| To evaluate the safety and tolerability of U3-1402 in subjects with advanced or metastatic CRC | 
Title: TEAEs and other safety parameters during the study*
 
Description: Descriptive statistics of safety endpoints
 
Time frame: From the time the subject signs the main study ICF and up to 40 (+ 7) days after the last dose of study drug (ie, 5 half-lives of the ADC/the follow-up period)
 
*Although this is a secondary objective, this is a primary outcome measure.
 | Incidence of TEAEs, SAEs, AESIs (ILD and elevation of aminotransferases and TBL), ECOG PS, vital sign measurements, standard clinical laboratory parameters. AEs will be coded using the most recent version of MedDRA and will be graded using NCI-CTCAE v5.0. | Safety |
| To evaluate HER3 protein expression in tumor tissue and its relationship with efficacy | 
Title: Correlation between HER3 protein expression (as determined by HER3 IHC assay) and efficacy
 
Description: Based on a descriptive summary of the efficacy endpoints and HER3 status, a correlative analysis between HER3 protein expression level (as determined by HER3 IHC assay) and efficacy may be performed.
 
Time frame: Efficacy data are collected at baseline, then from the start of study treatment until disease progression or death, lost to follow-up, or withdrawal of consent by the subject.
 
HER3 data are collected at baseline (archival and pre-treatment tumor biopsy) and at Cycle 2.
 | HER3 protein expression in tumor tissue (as determined by IHC) and correlation with efficacy | Efficacy/ Biomarker |

| Objectives | Outcome Measures | Endpoints | Category |
|---|--|--|---------------------|
| To assess the immunogenicity incidence against U3-1402 | 
Title: Immunogenicity
 
Description: ADA prevalence, incidence, and titer for U3-1402
 
Time frame: Data are collected from the start of study treatment until the end of treatment. Additional timepoints are specified in Table 13.1.
 | 
ADA prevalence: The proportion of all subjects having a confirmed positive ADA sample at any point in time.
 
ADA incidence: The proportion of subjects having treatment-emergent ADA.
 
ADA titer will be determined for confirmed ADA-positive samples.
 
Neutralizing antibodies: When neutralizing assay becomes available confirmed ADA-positive samples may be analyzed for neutralizing activity.
 | Immuno- genicity |

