9.2. Adverse Event Collection and Reporting

All clinical AEs occurring after the subject signs the main study ICF and up to 47 days after the last dose of study drug (ie, the follow-up period), whether observed by the Investigator or reported by the subject, will be recorded on the AE eCRF. When an AE of potential ILD (Section 9.3.1) is observed after 47 days since last dose of U3-1402, the AE (serious or non-serious) should be reported and recorded in AE eCRF if it is considered related to U3-1402. Medical conditions (including clinical laboratory values/vital signs that are out of range) that were diagnosed or known to exist prior to informed consent will be recorded as part of medical history.

All AEs, AESIs, events of overdose, and SAEs are to be reported according to the procedures in Section 9.5.

All clinical laboratory results, vital signs, and ECG results or findings should be appraised and documented by the Investigator to determine their clinical significance. Isolated abnormal clinical laboratory results, vital sign findings, or ECG findings (ie, not part of a reported diagnosis) should be reported as AEs if they are symptomatic, lead to study drug discontinuation, dose reduction, require corrective treatment, or constitute an AE in the Investigator's clinical judgment.

At each time point, the Investigator will determine whether any AEs have occurred by evaluating the subject. Adverse events may be directly observed, reported spontaneously by the subject or by questioning the subject (or, when appropriate, by a caregiver, surrogate, or the subject's legally authorized representative) at each time point. Subjects should be questioned in a general way, without asking about the occurrence of any specific symptoms. The Investigator must assess all AEs to determine seriousness, severity, and causality, in accordance with the definitions in Section 9.4. The Investigator and any qualified designees are responsible for detecting, documenting, and recording events that meet the definition of an AE or SAE and remain responsible for following AEs that are serious, considered related to the study drug or study procedures, or that caused the subject to discontinue U3-1402. The Investigator's assessment must be clearly documented in the study site's source documentation with the Investigator's signature.

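### ECG/QTcF, LVEF, ophthalmologic findings and ECOG PS are planned as listings only, so no rate or change from baseline independent of AE reporting will be produced.

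*Combined protocol and SAP*

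**What the plan says.** **Planned output.** Section 11.5.2.3 reads in full: "A listing of ECG data will be generated". Section 11.5.2.5 treats the remaining safety measurements the same way: "Listings of all other safety endpoints (eg, physical examination findings including ECOG PS, ECHO/MUGA, and ophthalmologic findings) will be generated".

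**Neighbouring sections.** For laboratory values, Section 11.5.2.2 adds to the descriptive statistics: "A shift table, presenting the 2-way frequency tabulation for baseline and the worst post-treatment value according to the NCI-CTCAE grade, will be provided". For vital signs, Section 11.5.2.4 states: "Descriptive statistics will be provided for the vital sign measurements and the change from baseline by scheduled time of evaluation, including EOT".

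**Stated objective.** Table 2.1 (Section 2) describes the safety outcome measure as "Descriptive statistics of safety endpoints". It names ECOG PS among the endpoints and marks the measure as a primary outcome measure.

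**Collection.** Table 13.1 schedules ECG, ECHO/MUGA and the ophthalmologic assessment at screening and EOT. Its footnotes allow further tests as clinically indicated. ECOG PS is also assessed on Day 1 of each cycle (Section 6.3.1).

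**Reason for collecting.** Section 1.2.2 says that, among other nonclinical toxicities, "cardiotoxicity, and renal toxicity were found in association with the administration of U3-1402". It also lists dry eye and keratitis as potential risks in humans.

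**The concern.** The protocol measures LVEF, QTcF and the eye before and after treatment, and Table 5.2 already sets numerical categories for LVEF and QTcF. Section 11.5.2 turns none of this into a count, a change from baseline or a shift. The reader of the study report would have the adverse event tables, which depend on what Investigators chose to report, and a by-subject listing.

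The weak spot is the EOT test. Section 9.2 says that isolated laboratory, vital sign and ECG abnormalities "should be reported as AEs if they are symptomatic, lead to study drug discontinuation, dose reduction, require corrective treatment", or if the Investigator judges them to be AEs. By EOT the drug has been stopped, so a change first seen there can rarely meet the discontinuation or dose-reduction trigger. If it is also asymptomatic and needs no treatment, Investigator judgment alone decides. At stake is whether the safety conclusion can give a systematic figure for cardiac and ocular change, including a figure of zero. Efficacy conclusions are not affected.

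**Working it through.** **1. Planned output side by side**

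| Measurement | Section | Planned output |
|---|---|---|
| Hematology, chemistry | 11.5.2.2 | Descriptive statistics, change from baseline, grade shift table |
| Vital signs | 11.5.2.4 | Descriptive statistics, change from baseline, listing |
| ECG/QTcF | 11.5.2.3 | Listing |
| LVEF, ophthalmologic findings, ECOG PS | 11.5.2.5 | Listing |

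No reason is given for the difference.

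**2. How an asymptomatic EOT change can reach a table**

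- ECG: Section 9.10 requires clinically relevant post-baseline abnormalities to be reported as AEs. Relevance is the Investigator's judgment.
- LVEF and eye: the rule for isolated findings in Section 9.2 does not name them. They fall under the general AE definition in Section 9.4.1, again with Investigator judgment.
- Once reported, the AE counts as a TEAE if it starts or worsens within 47 days after the end of treatment (Sections 11.5.2 and 11.5.2.1), which covers the usual EOT visit. It is then tabulated by SOC and/or PT and by worst grade.

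So a route exists, but it passes through a reporting decision. No planned table uses the measured values directly.

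**3. ECOG PS**

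Table 2.1 and Section 9.1 both name ECOG PS as a safety endpoint, and Table 2.1 places it under descriptive statistics. Section 11.5.2.5 plans a listing. A listing is not a descriptive statistic, so the two statements do not agree. LVEF, ECG and eye findings are not named in Table 2.1 or Section 9.1, so this conflict concerns ECOG PS only.

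**4. What a table could show (illustration)**

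The documents give no rate for an LVEF, QTcF or ocular change, so the true rate p is an assumption, shown at 2%, 5% and 10%. The number assessed, n, is set at 80 (planned total, Section 11.3) and at 36. The second is the total if neither cohort continues, and also stands for incomplete testing. Every one of the n subjects is taken to have a post-baseline test.

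Check against the plan: the exact (Clopper-Pearson) 95% interval for 4/80 is 1.4% to 12.3%, and for 8/80 it is 4.4% to 18.8%. Both match Table 11.3.

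Expected cases = n × p. P(at least one) = 1 − (1 − p)^n.

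| p | n = 80: expected | n = 80: P(≥1) | n = 36: expected | n = 36: P(≥1) |
|---|---|---|---|---|
| 2% | 1.6 | 1 − 0.98^80 = 80% | 0.72 | 52% |
| 5% | 4 | 1 − 0.95^80 = 98% | 1.8 | 84% |
| 10% | 8 | 1 − 0.90^80 > 99% | 3.6 | 98% |

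If no case were seen in 80 assessed subjects, the one-sided 95% upper limit would be 1 − 0.05^(1/80) = 3.7%. Section 11.5.2 asks for no such count or limit for these measurements.

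**The case against.** **Adverse event tables.** A reader might infer that an asymptomatic EOT decline appears in no safety table at all. The documents do not support that. Section 9.10 makes reporting mandatory for a clinically relevant ECG finding, with or without symptoms. Section 9.2 includes Investigator judgment, and its corrective-treatment trigger still applies after the drug is stopped. Section 9.4.1 can cover any unfavorable sign, and Section 5.4 puts dose modifications on the AE page of the eCRF. What remains is that every EOT route depends on a reporting decision.

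**Risk status.** It is tempting to call these known cardiac and eye risks. Section 1.2.2 supports less: cardiotoxicity is a nonclinical finding, and dry eye and keratitis are potential risks. Section 1.1.5 reports "troponin increased (3 [8.3%] subjects") at Grade 3 or higher in the lung cancer study, but the protocol does not name troponin increase as a risk. The AEs of special interest are ILD and hepatic events, and those are summarized.

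**Amount of data.** Each subject is not confined to one screening and one EOT value. Tests are repeated as clinically indicated, Table 5.2 calls for repeat LVEF in some categories, and an eye examination abnormal at discontinuation leads to a follow-up assessment. This adds data that could be tabulated; it does not supply a table.

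**Deferral to the SAP.** Sections 11.5.2 and 11.7 leave safety detail to a separate SAP, and the synopsis promises tabular safety output in general terms. Tables may be added there, so their absence from the final analysis cannot be asserted. This stands as a limit on the point. Still, Sections 11.5.2.3 and 11.5.2.5 do state a method, and that method is a listing.

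**Value of the tables.** In a single-treatment study with no testing planned, an EOT value often coincides with progression and cannot be attributed to the drug. That limits interpretation, but it applies equally to laboratory values and vital signs, which are summarized.

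**Conclusion.** The point holds as a cheap improvement, plus one internal conflict. Section 11.5.2 plans listings only for ECG/QTcF, LVEF, ophthalmologic findings and ECOG PS. Consequently, no systematic rate or change from baseline independent of AE reporting is planned for them, unlike for laboratory values and vital signs. For ECOG PS, Table 2.1 and Section 11.5.2.5 must be reconciled in any case.

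The size cannot be derived from the documents. The expected 1.6, 4 or 8 cases in 80 rest on assumed rates of 2%, 5% and 10% and on complete testing. They show that a table could be informative, not that a signal exists or would be missed. The textual finding rests on Section 11.5.2 as printed; the separate SAP could already have closed the gap.

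**What to change.** Keep the listings and add descriptive tables in Sections 11.5.2.3 and 11.5.2.5, or in the SAP with a cross-reference:

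- **LVEF and QTcF:** change from baseline to EOT and to the worst post-baseline value, unscheduled tests included. Give n (%) in the categories already printed in Table 5.2, plus a remainder category for subjects in none of them. The categories serve here for tabulation only.
- **Ophthalmologic findings:** normal/abnormal shift from baseline to EOT.
- **ECOG PS:** shift from baseline to the worst on-treatment value. This also brings Section 11.5.2.5 into line with Table 2.1.

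Use the number of subjects with a post-baseline test as the denominator in each table, and print it. If the separate SAP already contains these tables, align Section 11.5.2 with it.

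The cost is some wording and a few tables from data the schedule already collects. No assessment is added and no clinical rule changes. The drawbacks are slightly more output and denominators limited to subjects who were tested.

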11.5.3. Other Analyses

11.5.3.1. Pharmacokinetics

Data will be summarized by cohort if applicable.

PK Analyses as Secondary Objective

PK parameters will be listed and summarized using descriptive statistics.

Serum concentration-time data for U3-1402 (ADC, total anti-HER3 antibody and MAAA-1181a) will be listed, plotted, and summarized using descriptive statistics at each time point.

Exploratory PK Analyses

Serum concentration data may be used to perform a population PK modeling. The influences of intrinsic or extrinsic factor will be assessed in the population PK analysis. Population PK and exposure-response analyses for U3-1402 (ADC, total anti-HER3 antibody, and MAAA-1181a) may be performed to characterize the relationship between dose and exposure and between exposure and efficacy and/or safety endpoints. If performed, results of population PK analyses will be reported separately (ie, not in the CSR).

11.5.3.2. Pharmacodynamics

Not applicable.

11.5.3.3. Biomarker Analyses

HER3 protein expression in tumor tissue (as determined by IHC) may be summarized descriptively, and the correlation with efficacy parameters may be analyzed if data permits.

11.6. Interim Analyses

For each study cohort, review of the preliminary data from Part 1 will be used to determine whether to open Part 2. The decision to advance from Part 1 to Part 2 will be made separately in Cohort 1 and Cohort 2; the interim futility analysis will be conducted with approximately 24 subjects in Cohort 1 and approximately 12 subjects in Cohort 2 after all subjects have had the opportunity to complete two tumor assessments. The tumor assessment period may be extended if emerging data show responses are occurring later, or if the tumor assessment for the final evaluated subject in each cohort is delayed. At the time of the interim analysis for each cohort, enrollment into the respective cohort will be paused until the determination that criteria for advancement to Part 2 has been achieved. Note it is possible for the futility criterion to be passed before the above specified analysis timing. These analyses will be conducted based on BICR assessment in the FAS.

Cohort 1 Decision Criteria at Interim:

1. If at least 3 responders out of 24 subjects in Cohort 1 are observed, then further enrollment in this cohort may proceed.
2. If 0 or 1 responder out of 24 subjects in Cohort 1 is observed at the interim, then further enrollment in this cohort may stop.
3. If 2 responders out of 24 subjects in Cohort 1 are observed, then a decision will be made, after further review of the data, to either continue or stop further enrollment in this cohort.

Cohort 2 Decision Criteria at Interim:

1. If at least 2 responders out of 12 subjects in Cohort 2 are observed, further enrollment in this cohort may proceed after submission of a protocol amendment which includes the preliminary data from Cohort 2 Part 1.
2. If 0 responder out of 12 subjects in Cohort 2 is observed at the interim, then further enrollment in this cohort may stop.
3. If 1 responder out of 12 subjects in Cohort 2 is observed, then a decision will be made, after further review of the data, to either continue or stop further enrollment in this cohort. Further enrollment will be contingent upon submission of a protocol amendment which includes the preliminary data from Cohort 2 Part 1.

The exact decision rules will depend on the actual number of subjects at the respective interim analysis.

If the criterion to pass futility is met at interim for Cohort 2 but not Cohort 1, all data will be reviewed thoroughly to decide the next step for the study.

The criterion for interim analysis is constructed as follows: based on the interim data, if in a cohort there is less than 10% probability for the true ORR to be above 20% (clinically meaningful ORR), then U3-1402 is considered futile in this cohort and further enrollment may not be warranted. If there is at least 10% probability for the true ORR to be above 20% and at least 80% probability for the true ORR to be above 5% (ORR based on historical data)^{9,10} then promising efficacy is demonstrated in this cohort and further enrollment in this cohort may proceed.

If the true ORR is 20%, then the probability of observing at least 3 responders out of 24 subjects in Cohort 1 at the interim analysis will be 88.5% and the probability of observing at least 2 responders out of 12 subjects in Cohort 2 at the interim analysis will be 72.5%. If the true ORR is 5%, then the probability of observing 0 or 1 responder out of 24 subjects in Cohort 1 at the interim analysis will be 66.1% and the probability of observing 0 responders out of 12 subjects in Cohort 2 at the interim analysis will be 54%.

The determination of whether to advance a cohort to Part 2 of the study may also take into consideration the PK properties of U3-1402 among subjects enrolled in this study, and the subject or disease characteristics of enrolled subjects, among others. The decision to advance the study to Part 2 might be deferred based on the collective evaluation of such information. If indicated, the Sponsor may amend the protocol to evaluate other doses, dose regimens, or selected subject populations with advanced or metastatic CRC prior to advancing the study to Part 2.

